7.1 Schedule of Evaluations

The schedule of evaluations is summarized in Table 1 and described in detail below.

7.2 Visit 1 (Study Week - 2: Screening)

The following evaluations and tests will be performed:

- Preliminary Screening:
 - Obtain written informed consent process for study participant;
 - A sequential participant enrollment Screening number will be assigned to each patient who signs an informed consent;
 - Review inclusion/exclusion criteria, medical history including history of OAB/DO and prior/concomitant medications to assess eligibility for study treatment;
 - Determine proof of surgical sterilization or menopause;
 - Physical examination including urogenital examination and vital signs (with height and weight);
 - Complete screening if entry criteria are met on preliminary screening;
 - Bladder scan for residual volume and bladder capacity (prior to catheterization for urine culture);
 - Obtain urine for routine urine analysis: microscopic RBC and WBC, protein, glucose, nitrites, pH, and specific gravity;
 - Obtain a catheterized urine specimen for culture (after bladder scan);
 - Electrocardiogram;
 - Blood specimens for the following laboratory determinations:
 - Hematology: Complete Blood Count (CBC) with differential, platelet count, sedimentation rate (sed rate), PTT and PT.
 - Fasting chemistry: Blood Urea Nitrogen (BUN), creatinine, electrolytes (Na^+ , K^+ , Ca^{++} , Mg^{++} , CO_2 , Cl), albumin, alkaline phosphatase, ALT, AST, GGT, LDH, CPK, total bilirubin, total protein, C-reactive protein (CRP), antinuclear antibody (ANA), and glucose
 - Serum pregnancy test; FSH > 40 IU/L if last menstrual cycle not > 12 months prior to study enrollment and no hysterectomy or bilateral tubal ligation documented.
 - Blood hemoglobin A1c
- Provide patient with diary materials;
- Instruct the participant to complete daily voiding diaries for 7 days prior to next visit (if Visit 1A is scheduled within less than 1 week, then these diaries can still be used to review compliance, answer any questions participants have about diary completion, and

review inclusion criteria such as incontinence) and return with results at next visit including pads used for 72 hours prior to that visit (and clean pad to be used as baseline);

- Inform the participants that they should not take any antiplatelet drugs including over the counter NSAIDS and/or anticoagulant drugs, for at least 10 consecutive days prior to Visit 2.
- Schedule next study visit for Screening cystometry when Screening laboratory results are available (within at least 1 week).
- Depending on the screening results some participants may be allowed to rescreen, if they are unable to be dosed in a timely fashion due to some unforeseen factors (e.g., hospitalization for fracture, etc.). In this circumstance the same participant will be assigned a different screening number.
- If a participant meets all inclusion/exclusion criteria, but has a positive urine culture at screening, then all screening evaluations performed at V1 (and V1A) may be accepted after the participant is treated with appropriate antibiotics and the urine cultures come back negative. The maximum time frame would be approximately up to 4 weeks after screening V1A for acceptance of these screening evaluations after discussion with the sponsor or designee.
- If necessary due to scheduling issues, Visit 1A (i.e., screening cystoscopy) can overlap with Visit 1. In this case Visit 1A procedures not already performed at Visit 1 will be completed at Visit 1 (pads and diaries will not be available in this case). If V1A coincides with V1, then pad collection and diaries will not be completed prior to V1A and these must be checked for compliance at V2.

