4.2 Inclusion Criteria

1. Healthy women of 18 years of age or older and non-childbearing potential (i.e., prior hysterectomy or bilateral tubal ligation; last menstrual cycle more than 12 months prior to

study enrollment or serum FSH >40 IU/L if woman has not had a bilateral tubal ligation or hysterectomy).

2. Clinical symptoms of overactive bladder for 6 months or longer including at least one of the following:
 - a. Frequent micturition ≥ 8 times per 24 hrs
 - b. Symptoms of urinary urgency (the complaint of sudden compelling desire to pass urine, which is difficult to defer) or nocturia (the complaint of *waking* at night two or more times to void)
 - c. Urge urinary incontinence five or more incontinence episodes per week based on 7-day voiding diary. Urge urinary incontinence is defined as: the complaint of involuntary leakage accompanied by or immediately preceded by urgency.
3. Detrusor overactivity with ≥ 1 uncontrolled phasic contraction(s) of the detrusor of at least 5 cm/ H₂O pressure documented on cystometry at Screening Visit 1A (i.e., prior to study drug administration at Visit 2).
4. Bladder scan or direct catheter drainage demonstrating a residual volume of ≤ 200 ml
5. Non-response or response but poor tolerance to a previous treatment for symptoms of overactive bladder/urinary incontinence (e.g., anti-muscarinic/ anticholinergic agents, or Botox) or do not wish to continue these treatments.
6. Able to understand study requirements (i.e., literate in English), give written informed consent, and comply with all study procedures and requirements.

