4.3 Exclusion criteria

1. A woman with a positive serum (HCG) pregnancy test or lactating. (All women of child bearing years who have not had a hysterectomy will have a serum HCG.)
2. History of three or more culture documented recurrent urinary tract infections per year.
3. Current history of bladder outlet obstruction secondary to urethral stenosis, third degree cystocele, or obstruction from prior urethral sling surgery documented by cystoscopy, urothelial cancer, or other significant genitourinary disorders except incontinence (previous vesicle lithiasis or bladder stones that have been successfully removed are not an exclusion).
4. Current history or previous diagnosis of painful bladder syndrome (interstitial cystitis) with pain in the region of the pelvis, perineum, or lower abdomen relieved by voiding.
5. A urine culture (≥ 1000 colonies/ml) of a urinary pathogen from a catheterized urine obtained at screening.
6. Current history of neurological bladder dysfunction.
7. A life expectancy of less than 12 months.
8. Current history of Grade 2 or greater cystocele.

9. Stress urinary incontinence as determined by observation of the participant coughing while standing with a full bladder and/or response of 2 or 3 on the following Stress Urinary Incontinence question:

Do you experience leakage when laughing, coughing, lifting heavy objects or other types of discreet, moderately intense activities?

0= NONE: No leakage

1= MILD: Minimal leakage on rare occasions during these types of activities; easily tolerated; do not use pads for this.

2=MODERATE: Enough leakage that it requires occasional use of pads and may interfere with usual activity & tasks

3 =SEVERE: Extreme leakage & discomfort that stops all activity &/tasks and requires use of pads on all occasions

10. An indwelling urethral catheter or need for clean intermittent self-catheterization.
11. Any screening laboratory values outside of the normal laboratory range, as defined by the laboratory normal ranges and in the judgment of the investigator is considered clinically significant (hepatic biochemical markers \leq twice the upper limit of the normal reference range may be accepted with written consent of sponsor).
12. A hemoglobin A1c $>7\%$ in a person with diabetes.
13. A history of sickle-cell disease, sickle cell trait, or any other medical condition that, in the judgment of the investigator, would produce significant risk to the patient.

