7.3 Visit 1A (Study Day - 14 to -8): Screening Cystometry

- Review medical history and results of ECG and lab tests for eligibility and for any events which occurred **after** informed consent was signed at the screening visit. These events should be recorded on Medical History page;
- Review concomitant meds since last visit;
- Review voiding diaries and check compliance with completion (**do not enroll participant who is not compliant**) and for inclusion criteria such as incontinence;
- Collect and weigh pads used for 72 hours (**check for participant compliance**);
- Collect urine for urine culture prior to (using urodynamic catheter) and post cystometry (clean void). Also prior to cystometry, test sample of this urine by Dipstick™ in office to ensure there is no increase in leucocytes and nitrites;
- Have participant empty bladder and then perform baseline cystometry using preferably 7 or 8 French catheter (detrusor overactivity with ≥ 1 uncontrolled contraction(s) of the detrusor of at least 5 cm/ H₂O pressure must be documented during this Screening urodynamic testing) (see Appendix D);
- If participant is eligible, schedule Visit 2 at least 8 days (+2 days) after Visit 1A (they must complete 7 consecutive days of diaries prior to V2).

- Remind the participants that they should not take any antiplatelet/anticoagulant drugs including over the counter NSAIDS prior to the next visit.

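### A screening cystometry recorded with a positive urine culture may be accepted, and it then decides eligibility and serves as the only pre-dose reference for the five analysed cystometry parameters.

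*Protocol*

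**What the plan says.** - **Acceptance rule (Protocol 7.2).** With a positive screening culture, "all screening evaluations performed at V1 (and V1A) may be accepted after the participant is treated with appropriate antibiotics". A second condition is that repeat cultures have turned negative. The time limit runs from the cystometry visit: "The maximum time frame would be approximately up to 4 weeks after screening V1A for acceptance of these screening evaluations". The sponsor or its delegate must be consulted first.
- **Eligibility (Protocol 4.2, item 3).** DO must be "documented on cystometry at Screening Visit 1A".
- **Exclusion (Protocol 4.3, item 5).** A culture of at least 1000 colonies/ml "of a urinary pathogen from a catheterized urine obtained at screening" excludes. The criterion mentions no exception after treatment.
- **Check at V1A (Protocol 7.3).** Catheter urine is cultured and tested by dipstick before the cystometry, "in office to ensure there is no increase in leucocytes and nitrites".
- **Timing (Protocol 7.2).** The default is "Schedule next study visit for Screening cystometry when Screening laboratory results are available". The same section lets V1A coincide with V1 where scheduling requires it.
- **Analysis.** Cystometry is done at V1A, V5 and V8 (Protocol 6.2). SAP 9.2 analyses five overread parameters. The SAP synopsis defines baseline only for the safety parameters.

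**The concern.** One recording has two functions. It decides whether a woman has the DO needed to receive gene transfer, and it is the value from which her week 4 and week 24 cystometry changes are measured. The protocol treats a positive culture as a reason to exclude and checks for signs of infection just before the study, yet section 7.2 lets a recording made under those conditions stand. The infection is treated before dosing, so the bladder may have been in a different state at V1A than at V5 and V8. Any change due to that difference would enter the change from baseline and could not be separated from a treatment or placebo response. The cystometry endpoints bear directly on the stated efficacy hypothesis in Protocol 6.2, that the product reduces detrusor overactivity.

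**Working it through.** The plan gives no figure on this point to reproduce. The check is a trace through the text, followed by arithmetic on what one affected participant would do.

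**1. Does the rule reach the cystometry?** Yes. It names V1A, whose main evaluation is the cystometry (Protocol 7.3), and counts its limit of about 4 weeks from V1A. The requirement for negative cultures protects the dosing visit. It does not alter a recording already made, and no section asks for a repeat.

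**2. Is V1A the baseline?** By inference, yes. Of the three cystometry visits, V5 and V8 are post-dose. Protocol 7.3 calls the V1A study the baseline cystometry. The SAP does not say so.

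**3. Does any safeguard reject the recording?**
- *Exclusion 5* would, but 7.2 describes a woman who meets all criteria and still has a positive culture. The two can be read together only if 7.2 is an exception to exclusion 5, or if its undefined positive culture means something below that criterion's threshold. Neither is stated.
- *The dipstick* comes with no instruction to cancel or repeat the cystometry if it is positive. Protocol 6.9 says only that microscopy may be needed.
- *Waiting for V1 laboratory results* is the default, but the same-day option removes it. The culture taken at V1A itself cannot be reported before that day's recording.
- *Sponsor discussion* is required, but no criterion is attached.

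**4. Effect of one or two participants on DO present/absent.** Group sizes are 6 placebo, 6 per dose and 12 pooled active (SAP 3.2). Every woman enters with DO present, so the starting rate is 100%.
- One woman: 1/6 = 16.7 points; 1/12 = 8.3 points.
- Two women: 2/6 = 33.3 points; 2/12 = 16.7 points.

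A two-sided Fisher exact test is a simple yardstick here (the SAP plans a GEE logistic model):
- 1/6 against 0/6: p = 1.0.
- 2/6 against 0/6: 2 × C(6,2)/C(12,2) = 2 × 15/66, p = 0.45.
- 2/12 against 0/6: (66 + 15)/153, p = 0.53.

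**5. How likely is an affected recording?** The documents give no rate. Let q be an assumed proportion of participants with an accepted culture-positive V1A cystometry. At least one among n women has probability 1 − (1 − q)^n. Two groups of 6 have unequal counts with probability 1 − Σ P(X = k)², with X binomial(6, q).

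| q (assumed) | at least one of 18 | at least one of a given 6 | unequal counts, 6 v 6 |
|---|---|---|---|
| 5% | 60% | 26% | 40% |
| 10% | 85% | 47% | 58% |
| 20% | 98% | 74% | 71% |

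These are chances that such a recording exists, not that its values are wrong.

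**The case against.** **A reader might infer** that infection-driven contractions would be enrolled as idiopathic DO, that the benefit of antibiotics would then be read as a drug effect, and that one or two such women could create or hide an effect. The documents do not support this. They treat infection as a concern but never say that it provokes detrusor contractions or changes cystometry values. A positive culture need not mean active infection: Protocol 1.4.2 lists asymptomatic bacteriuria as an event in the earlier bladder study. Cystometry is also only one entry condition, alongside at least 6 months of symptoms and a history of prior treatment.

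**The rule looks deliberate.** Acceptance is discretionary and goes through the sponsor. Protocol 7.12 separately foresees a urinary infection found during screening. Blinded randomisation gives no expected direction between arms.

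**The reach is limited.** The voids-per-day result that SAP 9.1 names as primary efficacy uses the 7-day diary before V2, and the King's Health Questionnaire baseline is also V2. Efficacy is exploratory with nominal p-values (SAP 7.3).

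**A baseline fix is partial.** Nothing requires V5 or V8 recordings to be culture-negative, and four urinary infections in two of the five placebo women were reported in the earlier study.

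Most of this stands and limits the size of the claim. It does not remove the gap: no rule says whether a culture-positive recording counts. Randomisation does not reliably balance groups of 6, and it does not protect comparisons with a participant's own baseline.

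**Conclusion.** The point holds as a statement of what the protocol permits. A cystometry recorded with a positive culture may qualify a participant and become her reference value, against the sense of exclusion 5 and the pre-cystometry dipstick. That V1A is the baseline is an inference, because the SAP leaves the cystometry baseline undefined.

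Direction and size of bias are unknown. The shift of 16.7 points in a group of 6, or 8.3 in the pooled 12, assumes that one woman's DO status changes entirely for this reason. A shift of that size matters for a descriptive estimate in so small a trial, but one or two cases would not by themselves yield a significant difference. The diary-based primary efficacy result and the King's Health Questionnaire are not touched.

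**What to change.** 1. **Reconcile Protocol 4.3 item 5, 7.2 and 7.3.** Let the acceptance sentence in 7.2 cover laboratory, ECG and history results, but not a cystometry recorded with a positive culture. State whether 7.2 is an exception to exclusion 5.
2. **Tie V1A to the culture.** Schedule V1A after a negative V1 culture, as the default in 7.2 already implies. Where V1 and V1A fall on the same day, make acceptance of the cystometry conditional on the culture result.
3. **SAP.** Name V1A as the baseline for the cystometry parameters. Flag any participant whose V1A culture was positive and report the cystometry endpoints with and without her.

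The cost is protocol and SAP wording, a short scheduling delay and occasional loss of the same-day option. Protocol 7.12 already allows a longer screening period with sponsor approval when an infection is found. A repeat cystometry would be a further invasive, catheterised procedure, so whether to repeat a culture-positive study is for the sponsor to decide.

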7.3 Visit 1A (Study Day - 14 to -8): Screening Cystometry

- Review medical history and results of ECG and lab tests for eligibility and for any events which occurred **after** informed consent was signed at the screening visit. These events should be recorded on Medical History page;
- Review concomitant meds since last visit;
- Review voiding diaries and check compliance with completion (**do not enroll participant who is not compliant**) and for inclusion criteria such as incontinence;
- Collect and weigh pads used for 72 hours (**check for participant compliance**);
- Collect urine for urine culture prior to (using urodynamic catheter) and post cystometry (clean void). Also prior to cystometry, test sample of this urine by Dipstick™ in office to ensure there is no increase in leucocytes and nitrites;
- Have participant empty bladder and then perform baseline cystometry using preferably 7 or 8 French catheter (detrusor overactivity with ≥ 1 uncontrolled contraction(s) of the detrusor of at least 5 cm/ H₂O pressure must be documented during this Screening urodynamic testing) (see Appendix D);
- If participant is eligible, schedule Visit 2 at least 8 days (+2 days) after Visit 1A (they must complete 7 consecutive days of diaries prior to V2).

- Remind the participants that they should not take any antiplatelet/anticoagulant drugs including over the counter NSAIDS prior to the next visit.

7.4 Visit 2 (Study Week 0: Baseline - Administration of study drug)

[figure not shown]
Based on the participant fulfilling all eligibility criteria following the screening procedures (Visit 1 and Visit 1A) the participant will be considered eligible to receive study drug. If a participant is unable to receive test material because a clinically significant condition has evolved which, in the investigator's opinion, represents a potential safety risk, the participant will be considered a screen failure.

The following tests and evaluations will be performed on eligible participants:

- Review medical history, results of ECG, cystometry and lab tests for eligibility and for any events which occurred **after** informed consent was signed at the screening visits until prior to dosing at this visit. These events should be recorded on Medical History page. New events or changes reported **after** dosing must be recorded on the Adverse Event log;
- Review concomitant meds since last visit;
- Review voiding diaries and check compliance with completion (**do not enroll participant who is not compliant**) and inclusion criteria;
- Participants complete KHQ, SF-12 (QoL questionnaires) and global assessment of disease state **prior** to cystoscopy and study drug administration (Baseline questionnaires);
- Participants complete the ICIQ-SF (Baseline) **prior** to cystoscopy and study drug administration;
- Physical examination including urogenital exam and vital signs for changes since the screening visit **prior** to cystoscopy and study drug administration;
- ECG **prior** to cystoscopy and study drug administration (and 2 hours post administration of study drug). If abnormalities or clinically significant changes are noted from V1 screening ECG, then the investigator in conversation the Sponsor or designee will determine the participant's eligibility to proceed with dosing.
- Blood specimens for the following laboratory determinations **prior** to cystoscopy and study drug administration:
 - Hematology: Complete Blood Count (CBC) with differential, platelet count, sedimentation rate (sed rate). No chemistry testing required this visit.
- Obtain freshly voided urine specimen for culture **prior** to study drug administration using urodynamic catheter. Also test sample of this urine by Dipstick™ in office to ensure there is no increase in leucocytes and nitrites;
- Obtain urine and blood specimen for analysis of *hSlo* cDNA with PCR prior to cystoscopy and study drug administration (pre-dosing baseline) and 2 hour post-dosing;
- Collect and weigh pads used for 72 hours;

- Request (kit should be at the site at least 24 hours prior to drug administration) and Assign participant kit number;
- Drain the participant's bladder through the transurethral catheter. Administer local anesthesia through the 7 or 8 French catheter using an instillation of 40 ml of 2% lidocaine and 2 % xylocaine gel in the urethra before insertion of the cystoscope. Once the catheter is removed administer the assigned randomized dose of study drug by sterile aseptic technique as follows. Approximately 10- 20 minutes after the local anesthetic has been administered the cystoscopic device can be inserted. Inject intravesically into the detrusor muscle, under cystoscopic control, 4 ml (for 16000 µg group) or 6 ml (for 24000 µg group) of randomized selected drug. The randomized drug is injected into the detrusor muscle via a rigid cystoscope (preferably 18 to 21 French), avoiding the trigone (see Figure 6 below). The bladder should be instilled with enough saline to achieve adequate visualization for the injections, but over-distension should be avoided. The injection needle should be filled (primed) with approximately 1 mL of study drug prior to the start of injections (depending on the needle length) to remove any air. The needle should be inserted approximately 2 mm into the detrusor, and 20 injections of either 0.2 ml (for 16000 ug dose) or 30 injections of 0.2 mL (for the 24000 µg dose) each (total volume of 4 or 6 mL, respectively) should be spaced approximately 1 cm apart (see Figure 6, below). For the final 5 injections of each dose, PBS 20% sucrose should be used in the injection syringe so that the product in the needle is delivered. After the injections are given, the bladder should be drained.

Figure 6. Bladder Injection Sites

- The time of voiding following drug administration will be recorded. The participant will be observed in the clinic for two hours after the bladder injections are completed. During that time blood pressure and pulse will be measured and recorded by the nurse every 15 minutes. The participant will be asked if there is any persistent pain/irritation in the bladder/urethra and will be treated symptomatically, if needed. The participant will be asked if they have experienced any new symptoms or problems they want to report to the investigator or study personnel. Emergency equipment for resuscitation will be immediately available in the event of an unexpected serious reaction to the study drug;
- Participants are required to stay at the study site for at least 2 to 3 hours after dosing. They may be asked stay longer if the investigator believes it is necessary.

- Collect first voided urine (clean void) after drug administration for culture prior to discharge;
- Provide participant with diary materials;
- Provide participant with prophylactic antibiotics prior to discharge (to take immediately and for the 2 days following Visit 2)
- Instruct the participant to complete daily voiding diaries for 7 days prior to next visit and return with results at next visit, including pads used for 72 hours prior to that visit (and clean pad to be used as baseline).

7.5 1-Day and 3-Day Post Visit 2 Telephone Contact

One day and three days (3 days \pm 1 day) following Visit 2 (when the participant received the bladder injections) she should be contacted to assess for any problems she may be experiencing. The patient must be asked in a general fashion if she has had any complaints since her last visit. All adverse events should be documented on the adverse event E-CRF. The patient may be brought back to the clinic sooner than Visit 3 if required.

